6.2.2 Vaginal pH Determination

For pH determination, a reactive pH strip will be used. On each occasion, the investigator will insert the strip into the vagina and moisten it as much as possible with the vaginal wall

secretions. Once adequate wetting has been achieved, the colors on the strip will be checked against a standard pH scale (provided by the manufacturer) to determine the pH value. The reading should be made while the strip is still moist. The strips will be discarded appropriately once the pH has been recorded.

Vaginal pH determination will be performed at Screening Visit, at the Week 3 Visit, and at the Week 12/Early Termination Visit.

6.2.3 Evaluation of Vaginal Symptoms and Signs

6.2.3.1 Evaluation of Symptoms

At study visits the investigators will interview the subjects on the presence and intensity of the symptoms of vulvovaginal atrophy they have. Study subjects will self-assess their symptoms and report their assessments to the investigators to be recorded. .

The symptoms evaluated in this study include vaginal dryness, pruritus or itching, burning, dyspareunia, and dysuria.

Each symptom will be scored by the subject using a numeric scale from 0 to 3, as shown below:

- 0 - Absent: The symptom is not present.
- 1 - Mild: The symptom is of mild intensity,
- 2 - Moderate: The symptom is of moderate intensity
- 3 - Severe: The symptom is severe in intensity.

The presence and intensity of vaginal symptoms of vulvovaginal atrophy will be assessed at the following visits: Screening (vaginal dryness only); Baseline (pruritus or itching, burning, dyspareunia, and dysuria); Week 3 (all 5 symptoms: vaginal dryness, pruritus or itching, burning, dyspareunia, and dysuria); and Week 12/Early Termination (all 5 symptoms: vaginal dryness, pruritus or itching, burning, dyspareunia, and dysuria).

Specific to the evaluation of dyspareunia, women will be also asked if they have had sexual activity with penetration during the study period.

6.2.3.2 Evaluation of Signs

The presence and severity of most typical signs of vulvovaginal atrophy will be recorded according to the visual inspection of the vagina as performed by the investigator.

The signs evaluated in this study include vaginal mucosa with flattening of folds or thinning, dryness of the mucosa, pallor of the mucosa, friability of the mucosa, and presence of petechiae.

Each one of these signs will be scored by the investigator on a numerical Likert scale as follows:

0 – Absent: The sign is not present.

1 – Mild: The sign is present and is considered a mild alteration.

2 – Moderate: The sign is present and is considered a moderate alteration.

3 – Severe: The sign is present and is considered a severe alteration.

The presence and intensity of all these 5 signs of vulvovaginal atrophy will be assessed at the Baseline Visit, the Week 3 Visit, and at the Week 12/Early Termination Visit.

6.2.3.3 Evaluation of Global Symptom Score

A Global Symptom Score will be obtained by summing the numerical scores of all symptoms at different time points: Screening/Baseline, Week 3 and Week 12/Early termination visit. Thus, the Global Symptom Score will range at Screening/Baseline between 2 (at least moderate vaginal dryness as the only symptom) to 15 (all five studied symptoms severe in intensity). At Weeks 3 and Week 12/Early Termination visits the Global Symptom Score can range between 0 (no symptoms) and 15 (all symptoms severe in intensity). The Global Symptom Score will be evaluated when all 5 individual symptoms scores are available at a given time point.

6.2.4 Evaluation of Global Efficacy

At the Week 12/Early Withdrawal Visit, the subject will be interviewed by the investigator on her perception of the global efficacy of the therapy received over the completed study period. Global efficacy is defined as the subject's perception of the effect of the treatment on her vaginal-related symptomatology.

The subject will be asked to rate the global efficacy of the treatment as: highly efficacious, efficacious, non-efficacious, or detrimental.

6.3 Safety Assessments

6.3.1 Clinical Laboratory Assessments

At the Screening and Week 12/Early Termination Visits, blood and urine specimens will be collected under fasting conditions for the following measurements:

- Hematology: Standard hematology panel plus prothrombin time, activated thromboplastin partial time, fibrinogen, and antithrombin III/protein C/protein S. Factor V Leiden will be performed at either screening visit or week 12/ET visit if not previously obtained at screening.
- Blood chemistry: Standard chemistry panel including albumin, alanine aminotransferase, aspartate aminotransferase, creatine phosphokinase, bilirubin, creatinine, total protein, uric acid, blood urea nitrogen, glucose, and lipids (cholesterol, high-density lipoprotein, low-density lipoprotein, and triglycerides)
- Hormones: Estradiol, estriol, estrone, follicle-stimulating hormone (FSH), and luteinizing hormone (LH)
- Urinalysis: Standard urinalysis including testing for presence of blood, glucose, ketones, and protein, with microbiological analysis

A laboratory manual will be provided to each site, detailing procedures for sample collection, storage, and shipment. Samples will be destroyed at the end of the study.

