The physiological effect of estrogens is complex: they exert their action through the activation of specific nuclear receptors, and different estrogens bind with different affinities to their receptors. Two subtypes of estrogen receptors (ERs) have been identified; these subtypes are ER α and ER β , with different tissue distributions, although there is some overlap in their expression, as ER α is most abundantly expressed in the endometrium, breast, and ovarian stroma. The relative binding affinities of different estrogens for their receptors has been investigated in different models against 17 β -estradiol, the most potent natural estrogen. In this sense, the binding affinities of estriol to ER α and ER β have been shown to be 14% and 21% of those of estradiol, respectively (Gruber CJ, 2002). Also, the differential expression of receptors in tissues results in topological (tissue) differences in the affinities of the various estrogens. Compared to estradiol, estriol shows a relatively high affinity for the receptors in bladder and vaginal tissue, but relatively low affinity for receptors in the uterine and breast tissue (Bergink EW, 1984). The lower affinity in the uterus results in minimal or no uterotrophic influence with estriol exposure (Takahi K, 2000) (Raz R, 1993) (Padwick ML, 1986) (Reynolds TM, 1993). The non-uterotrophic effect is also attributed, in part, to its relatively short duration of nuclear receptor binding and rapid plasma clearance (Cardozo L, 1998) (van Haaften M, 1997).

Other claimed advantages of estriol over other natural estrogens include a protective effect against development of breast cancer, minimal mitogenic activity, less effect on plasma lipids and coagulation factors/platelets, and an ability to reduce/block the uterotrophic activity of other estrogens (competition with receptor binding) (Takahi K, 2000) (Padwick ML, 1986) (Hayashi T, 2000) (Nakayama H, 1999).

Estriol formulations have been marketed since 1958 for the treatment of vulvovaginal atrophy in more than 50 countries worldwide, including all European countries, but not the United States. Topical (vaginal) formulations are currently available as creams (containing 1 mg estriol/1 g cream) or as ovules (containing 0.5 mg estriol). Local vaginal estrogen therapy can also be administered in the form of estradiol vaginal tablets or vaginal creams, estradiol-releasing vaginal rings and conjugated estrogen-based vaginal creams.

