3.1 Study Design

This study is a double-blind, randomized, dose-ranging, placebo-controlled multicenter study with four parallel groups. Approximately 25 sites in Europe will be included in the study. The study setting will include academic hospitals and gynecological clinics. The study population is postmenopausal women who report moderate to severe vaginal dryness as their most bothersome symptom in addition to other symptoms and/or signs of postmenopausal vulvovaginal atrophy.

After providing informed consent, potential subjects will be evaluated during the screening period to determine if they are eligible to participate in the study. A screening identification number will be assigned to each eligible subject according to their order of arrival into the study at screening visit. Subjects who meet all of the inclusion criteria (see Section 4.1.1) and none of the exclusion criteria (see Section 4.1.2) will be randomized into the study. A total of 280 subjects will be enrolled and randomly allocated to one of the four treatment groups (0.005%, 0.002%, or 0.0008% estriol vaginal gel or placebo vaginal gel); the allocation to treatment group will be 1:1:1:1. A blocked randomization across the entire study (i.e. all sites as a whole) will be used. Subjects will be assigned a randomization code according to their order of arrival into the study at the Baseline Visit. Initial treatment consists of daily vaginal administration of 1 gram of randomly-assigned estriol gel or placebo gel using the supplied applicator. After 21 days of daily administration, treatment will continue with twice-weekly administration up to Week 12 (i.e., Mondays and Thursdays).

The duration of trial participation for each woman is expected to be approximately 20 weeks (from Screening to End-of-Study phone call) although the time on study drug will be approximately 12 weeks. Subject completion is defined as the completion of all phases of the study, including the End-of-Study phone call to be performed for safety purposes at Week 16.

An overview of the study visit procedures is given in the Schedule of Events (Table 1). Details of specific procedures and testing are provided in Section 6.

Table 1: Schedule of Events

Procedure	Screening Visit	Baseline	Week 3	Week 8	Week 12/ Early Termination	Week 16/ End of Study Phone Call
Visit Window (days)	-30 to -1	1	21 ±3	56 ± 5	84 ± 5	112 ± 5
Informed consent	X					
Randomization		X				

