e	Laboratory testing performed under fasting conditions at Screening and Week 12 includes: standard hematology panel plus prothrombin time, activated thromboplastin partial time, fibrinogen, antithrombin III/protein C/protein S; standard chemistry panel (glucose, cholesterol, high-density lipoprotein, low-density lipoprotein, triglycerides albumin, alanine aminotransferase, aspartate aminotransferase, creatine phosphokinase, bilirubin, creatinine, total protein, uric acid, blood urea nitrogen); hormones (estradiol, estriol, estrone, follicle-stimulating hormone, luteinizing hormone); and standard urinalysis with microbiology. Factor V Leiden testing will be performed only at screening visit (or Week 12/ET visit if not obtained at screening)					
f	AEs and SAEs will be recorded from screening (post ICF signature) and subsequently at every study visit and up to 30 days post last study drug administration. Tolerability of study drug will be evaluated at weeks 3, 8, 12, and 16.					
g	For the evaluation of symptoms and signs, each symptom and each sign will be graded as: 0=absent; 1=mild; 2=moderate; 3=severe					
h	Signs and symptoms other than vaginal dryness to be evaluated are the following: Symptoms: dyspareunia, pruritus or itching, burning, dysuria. Signs: pallor, friability, thinning or flattening of folds, presence of petechiae, and dry mucosa					
i	Global efficacy will be assessed as: highly efficacious, efficacious, non-efficacious, detrimental					
j	Global acceptability will be assessed as: excellent, good, acceptable, unacceptable					
k	The investigator will administer the first study medication or will supervise the patient doing the administration					
l	Medication kits will be dispensed via IWRS					

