6.2.4 Treatment Exposure and Compliance

Study treatment exposure and compliance will be summarized by treatment group and overall for the Safety population.

Study Treatment Data

Subjects are instructed to bring their used and unused study treatment and unused applicators to the Week 3, Week 8 and Week 12 visits. All used applicators will be discarded by the subjects in their normal household waste. Compliance will be evaluated at the site, by reviewing the study treatment and the returned supplies. The following data related to administration of study treatment will be collected:

- [A] The date of first administration of study treatment will be captured on the 'Study Drug Administration – Baseline' page of the eCRF.
- [B] Ongoing study treatment data will be captured at the Week 3, Week 8 and Week 12 visits on the 'Study Drug Administration and Compliance – Cumulative' page of the eCRF. This log page includes, for each kit number: the date dispensed, the date returned, whether the tube of gel was returned, the number of applicators returned, the number of applicators used and the number of applicators lost/missed/damaged.
- [C] When the subject completes or discontinues from the study, the date of last administration of study treatment will be captured on the 'End of Study' page of the eCRF.

Exposure

Extent of exposure to study treatment is defined as:

$$\text{Extent of Exposure (days)} = \text{Date of Last Administration of Study Treatment}^{[C]} - \text{Date of First Administration of Study Treatment}^{[A]} + 1$$

The date of last administration of study treatment will be taken from the 'End of Study' page of the eCRF wherever available. If this is missing or not known, the date of last administration of study treatment will be assumed to be the latest date that a kit is returned on the 'Study Drug Administration and Compliance – Cumulative' page^[B] of the eCRF.

If no kits were dispensed according to the 'Study Drug Administration and Compliance – Cumulative' page^[B], but the study treatment was administered at Baseline according to the 'Study Drug Administration – Baseline' page^[A], the date of last administration of study treatment will be assumed to be equal to the date of first administration of study treatment, i.e. exposure will be calculated as equal to 1 day.

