6.4.5 Laboratory Parameters

Clinical laboratory tests will be performed under fasting conditions at the Screening and Week 12 / Early Termination visits. The following parameters will be assessed:

- Hematology:
 - Basophils
 - Eosinophils
 - Lymphocytes
 - Monocytes
 - Neutrophils
 - Basophils/Leukocytes
 - Eosinophils/Leukocytes
 - Lymphocytes/Leukocytes
 - Monocytes/Leukocytes
 - Neutrophils/Leukocytes
 - Hematocrit
 - Hemoglobin
 - Platelets
 - Erythrocytes
 - Leukocytes
 - Factor V Leiden (either at Screening or at Week 12 / Early Termination if not previously obtained at Screening)
- Blood Chemistry:
 - Albumin
 - Alanine Aminotransferase
 - Aspartate Aminotransferase
 - Blood Urea Nitrogen
 - Creatine Kinase
 - Creatinine
 - Glucose
 - Bilirubin
 - Protein
 - Urate
 - Triglycerides
 - Cholesterol
 - Cholesterol: High-Density Lipoprotein
 - Cholesterol: Low-Density Lipoprotein
- Urinalysis:
 - pH
 - Specific Gravity
 - Clarity
 - Colour
 - Protein
 - Glucose
 - Occult Blood

- Leukocytes – assessed routinely by dipstick; sediment method is used to confirm a positive dipstick result. If both dipstick and sediment results are present at the same visit, the sediment result will be used any applicable statistical summaries.
- Bilirubin
- Ketones
- Urobilinogen
- Nitrates
- Erythrocytes
- Bacteria
- Casts
- Crystals
- Epithelial Cells
- Yeast Cells
- Coagulation:
 - Activated Partial Thromboplastin Time
 - Prothrombin Time
 - Protein C
 - Protein S
 - Thrombin/Antithrombin III
 - Fibrinogen
- Endocrinology (Hormones):
 - Estradiol
 - Estriol
 - Estrone
 - Follicle Stimulating Hormone (FSH)
 - Luteinizing Hormone (LH)

The samples will be analyzed by the central laboratory, [REDACTED] Reference ranges are available for all applicable parameters in Appendix I of the [REDACTED] Laboratory Manual. All parameters will be summarized in conventional units as provided by [REDACTED]

The absolute values of continuous laboratory parameters will be summarized at each visit by treatment group and overall, using summary statistics for continuous variables. Change from Baseline (Screening) values will also be summarized at the Week 12 / Early Termination visit. Categorical laboratory parameters will be listed only.

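### One untimed on-treatment estriol sample, pooled at Week 12/Early Termination, gives a diluted mean change and cannot show peak or daily-phase exposure

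*Protocol*

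**What the plan says.** **Sampling.** Protocol 6.3.1 reads: "At the Screening and Week 12/Early Termination Visits, blood and urine specimens will be collected under fasting conditions for the following measurements". The list that follows includes five hormones: estradiol, estriol, estrone, FSH and LH. Protocol 6.1.3 and 6.1.4 list no blood draw at Week 3 or Week 8. Fasting is the only condition on the draw in the protocol or SAP.

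**Dosing.** Protocol 3.1: "After 21 days of daily administration, treatment will continue with twice-weekly administration up to Week 12". Monday and Thursday are the example days, and Protocol 5.4.1 has the gel applied at bedtime after the first dose.

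**Visit timing.** Protocol 6.1.5 sets the Week 12 visit by calendar, with 5 days' tolerance either way and no link to the last application.

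**Pharmacology.** The Protocol Introduction describes estriol's "relatively short duration of nuclear receptor binding and rapid plasma clearance", and says that estriol is not converted to estradiol or estrone.

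**Analysis.** Change from Baseline in hormone levels is a named safety endpoint (Protocol 7.4). SAP 6.4.5: "Change from Baseline (Screening) values will also be summarized at the Week 12 / Early Termination visit". It adds low/normal/high shift tables. Nothing is broken down by time since last application.

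**Dates held.** SAP 6.2.4 says "the date of last administration of study treatment will be captured on the 'End of Study' page of the eCRF". No clock time is mentioned.

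**The concern.** If a drug clears quickly from plasma, its measured level depends heavily on how long ago it was applied. Here that interval is left to the weekday of the visit, and the summary averages over all intervals. Early-termination samples join the same summary. Some of these may be drawn well after the last dose, since Protocol 4.2.2 allows two telephone calls and then a registered letter to bring a subject back.

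The Protocol Synopsis rests the trial's rationale on lower estrogen exposure per application. A study report could state that estriol did not change without saying what was tested. A flat mean could reflect low absorption, or it could reflect many draws taken days after an application. It would also say nothing about the first three weeks, when the gel is used daily.

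**Working it through.** **1. The plan's own application counts.** Protocol 5.4.1 expects 21, 10 and 8 applications in the three dispensing periods. Check: 21 daily, then 5 weeks × 2 = 10, then 4 weeks × 2 = 8, total 39. The SAP 6.2.4 algorithm agrees: 21 + (63/7) × 2 = 39. The application rate is 7 per week in the daily phase and 2 per week when the scheduled sample is taken, a ratio of 7/2 = 3.5.

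**2. Time from application to draw.** Assumed: Monday/Thursday application at 22:00, draw at 10:00.

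| Draw day | Hours since application |
|---|---|
| Monday | 84 |
| Tuesday | 12 |
| Wednesday | 36 |
| Thursday | 60 |
| Friday | 12 |

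With draws spread evenly over these days, 2/5 = 40% fall within 24 h and 3/5 = 60% fall later. Over all seven days, 5/7 = 71% fall later. These shares do not change for bedtimes of 21:00-23:00 and draws at 08:00-12:00; the next-morning interval then ranges from 9 to 15 h. The visit window spans 10 days (±5), longer than either dosing interval (3 or 4 days), so any of these intervals can occur.

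**3. Effect on the arm-level summary.** The documents give no half-life, so *h* is varied from 4 to 24 h. Assume first-order decline and ignore carry-over from earlier applications. The level relative to the 12-hour level is 2^(−(t − 12)/h).

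| h (hours) | Mon (84 h) | Tue, Fri (12 h) | Wed (36 h) | Thu (60 h) | Mean of five days | Median |
|---|---|---|---|---|---|---|
| 4 | 0.000 | 1 | 0.016 | 0.000 | 0.40 | 0.016 |
| 6 | 0.000 | 1 | 0.062 | 0.004 | 0.41 | 0.062 |
| 12 | 0.016 | 1 | 0.25 | 0.062 | 0.47 | 0.25 |
| 24 | 0.125 | 1 | 0.50 | 0.25 | 0.575 | 0.50 |

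Example for h = 24: (0.125 + 1 + 0.50 + 0.25 + 1)/5 = 2.875/5 = 0.575.

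**4. Early termination.** The planning assumption in Protocol 7.5 is 18% drop-out, about 70 − 57 = 13 subjects per arm. Any of them who attend an early-termination visit add a sample to the same summary, at whatever interval has passed since their last dose.

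**The case against.** Several counter-arguments have force.

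- **The signal survives.** A reader might infer that estriol will read near baseline whatever the true exposure. The documents do not support that. About 40% of weekday draws fall near 12 h. SAP 6.1.1 plans quartiles, minimum and maximum alongside the mean, and with 40% of values in the next-morning group the upper quartile and maximum would largely reflect it. Hormone values are also listed by subject (Listing 16.2.8.5). This stands.
- **The size is assumed.** The documents give neither a half-life nor an assay limit, and slow release from a muco-adhesive gel is not modelled. This stands: the direction follows from the documents, the percentages from assumptions.
- **It concerns estriol only.** Because the protocol says estriol is not converted to estradiol or estrone, the clearance argument does not carry over to them. This stands. Week 12 endometrial biopsy and ultrasound do not use this hormone summary.
- **There is other evidence, and some material is unseen.** The SAP Introduction reports very low systemic exposure for the 0.005% gel in an earlier study. This trial has no pharmacokinetic objective. The laboratory manual, which was not available, might set a draw time. These points lower the stakes, but the SAP would still plan no analysis by time since application.
- **Early termination before Week 3** would sample in or just after the daily phase. That is true, but such samples are incidental and would sit unmarked in the pooled summary.
- **A tempting remedy does harm.** Booking Week 12 for the morning after an application would also move the dryness, pH and smear assessments closer to gel use. The SAP Introduction credits the gel itself with a hydrating effect, and the placebo is the same gel without estriol (Protocol 5.3). That trade-off is not worth making for a descriptive safety value.

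**Conclusion.** The point holds in limited form. Estriol has one scheduled on-treatment draw, in the twice-weekly phase, at no set interval after an application, and SAP 6.4.5 pools every such sample with early-termination samples. About 60% of weekday draws would fall more than 24 h after an application, and the mean rise would be diluted to roughly 40-57% of the 12-hour level. Those figures rest on the example Monday/Thursday bedtime schedule, morning draws spread evenly over weekdays, first-order decline and an assumed half-life of 4-24 h.

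The draw cannot characterize peak or daily-phase exposure, and a null mean change is not evidence of no absorption. No co-primary result, gatekeeping step or minimal-effective-dose conclusion depends on this. It is a worthwhile, inexpensive improvement to the safety reporting.

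**What to change.** Amend SAP 6.4.5 before unblinding:

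- Split the Week 12/Early Termination estriol summary and shift table, in all four arms, by sample date minus last-administration date: next-morning samples (difference of 1 day) versus later ones. Take shift-table percentages within each group.
- Show off-drug early-termination samples separately. A workable cut is more than 4 days, the longest interval in the example schedule. Flag any early-termination sample taken before Week 3.
- Use recorded dates only. SAP 6.2.4 replaces a missing last-administration date with the latest kit-return date, which may be the visit day itself and would give a false interval. Report samples with an unknown interval, or with a recorded application on or after the sample date, as unclassified.
- Base any systemic-exposure statement on the next-morning group, and state that it covers the twice-weekly phase only.

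If the eCRF can still take it, add the clock time of the last application before the draw. Estradiol and estrone need no split, and visit booking should stay as planned.

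The cost is one extra table split and smaller groups. At 40% next-morning draws, that group would be about 0.40 × 70 = 28 per arm if everyone gives a sample, or 0.40 × 57 ≈ 23 with the planned drop-out. No blood draw is added and the efficacy assessments are untouched. The daily phase stays unsampled, which is why the limit on the exposure statement is needed.
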